7.1.1. Temporary Discontinuation

See Section 6.6 for stopping rules and toxicity management.

7.2. Subject Discontinuation/Withdrawal from the Study

Subjects are free to discontinue their participation in the study at any time and without prejudice to further treatment. The Investigator must withdraw any subject from the study if that subject requests to be withdrawn, or if it is determined that continuing in the study would result in a significant safety risk to the subject.

Subjects who discontinue study drug or are withdrawn from the study prior to the first efficacy endpoint will not be replaced.

The subject's participation in the study may be discontinued due to the following reasons:

- Request of Investigator
- Life-threatening event or death
- Subject withdrew consent
- Subject is lost-to-follow-up

The subject may discontinue study medication due to the following reasons:

- Request of Investigator
- AE
- Treatment failure
- Subject is non-compliant with study procedures or study protocol
- Request of regulatory authority
- Pregnancy
- Other (to be specified in the electronic case report form; eCRF)

7.3. Lost to Follow up

A subject will be considered lost to follow-up if he or she repeatedly fails to return for scheduled visits and is unable to be contacted by the study site.

The following actions must be taken if a subject fails to return to the clinic for a required study visit:

- The site must attempt to contact the subject and reschedule the missed visit as soon as possible and counsel the subject on the importance of maintaining the assigned visit schedule and ascertain whether or not the subject wishes to and/or should continue in the study.
- Before a subject is deemed lost to follow up, the Investigator or designee must make every effort to regain contact with the subject (where possible, 3 telephone calls and, if necessary, a certified letter to the subject's last known mailing address or local equivalent methods). These contact attempts should be documented in the subject's medical record.
- Should the subject continue to be unreachable, he/she will be considered to have withdrawn from the study.

Discontinuation of specific sites or of the study as a whole are handled as part of Appendix 1 in Section 10.1.8.

8. STUDY ASSESSMENTS AND PROCEDURES

- Study procedures and their timing are summarized in the SoA. Protocol waivers or exemptions are not allowed.
- Immediate safety concerns should be discussed with the investigator immediately upon occurrence or awareness to determine if the subject should continue or discontinue study intervention.
- Adherence to the study design requirements, including those specified in the SoA, is essential and required for study conduct.
- All screening evaluations must be completed and reviewed to confirm that potential subjects meet all eligibility criteria. The investigator will maintain a screening log to record details of all subjects screened and to confirm eligibility or record reasons for screening failure, as applicable.
- Procedures conducted as part of the subject's routine clinical management (eg, blood count) and obtained before signing of the ICF may be utilized for screening or baseline purposes provided the procedures met the protocol-specified criteria and were performed within the time frame defined in the SoA.

8.1. Efficacy Assessments

Planned time points for efficacy assessments are provided in the SoA.

8.1.1. Complete Pathologic Response (pCR)

The primary endpoint of this study is pCR, defined as no viable tumor on histologic assessment at definitive surgery ([Tetzlaff, 2018](#)). pCR will be evaluated locally by a certified surgical pathologist.

8.1.2. Response Evaluation Criteria in Solid Tumors (RECIST) v1.1 and immune RECIST (iRECIST)

Secondary efficacy endpoints will be evaluated using RECIST v1.1 ([Eisenhauer, 2009](#)) as described in Section [10.7.1 \(required\)](#) and iRECIST (optional), as described in Section [10.7.2](#).

Radiographic imaging will be assessed locally by the Investigator during the neoadjuvant phase (preoperative, unconfirmed); during the adjuvant phase, radiographic imaging and local assessments will be done only if feasible (as tumor is resected during surgery).

Disease staging will be collected at original diagnosis and at screening for this protocol, prior to any treatment initiation.

8.1.3. Lesion Photographs and Unidimensional Clinical Measurements

Lesions photographs and unidimensional clinical measurements will be done as specified in SoA. Lesions will be numbered identically for each visit, each lesion will also be labelled as target, non-target, or new lesions ([Table 8](#)). At all study visits, lesion photography will always be done with a caliper/ruler and lesion identification on all accessible clinically measure lesions.

8.2. Safety Assessments

Planned time points for all safety assessments are provided in the SoA.

8.2.1. Medical History and Concomitant Medications

Any diseases in the prior three years including any co-morbid conditions requiring active treatment as well as significant surgeries will be documented in the medical history of the eCRF. Abnormal physical examination finding and/or the diagnosis of concomitant disease resulting from assessment at screening must be also documented in the medical history section.

Information on all interventions (systemic therapy, surgery, radiation treatment) related to the subject's melanoma cancer will also be collected.

Concomitant medication is defined as any prescription or over-the-counter preparation, including vitamins and supplements. Corticosteroids, immunosuppressant and/or hormonal replacement therapies that the subject is receiving at the time of enrollment or receives during the study must be recorded along with:

- Reason for use
- Dates of administration including start and end dates

8.2.2. Eastern Cooperative Oncology Group (ECOG) Performance Status

The ECOG Performance Status will be used to assess subjects' performance status by the same study staff ([Table 2](#)). The performance status will be assessed as specified in the SoA (Section [1.3](#)).

Table 2 ECOG Performance Status

ECOG PERFORMANCE STATUS	
Grade	ECOG
0	Fully active, able to carry on all pre-disease performance without restriction
1	Restricted in physically strenuous activity but ambulatory and able to carry out work of a light or sedentary nature, e.g., light house work, office work
2	Ambulatory and capable of all self-care but unable to carry out any work activities. Up and about more than 50% of waking hours
3	Capable of only limited self-care, confined to bed or chair more than 50% of waking hours
4	Completely disabled. Cannot carry on any self-care. Totally confined to bed or chair
5	Dead

8.2.3. Durable Procedural Pain Assessment

[figure not shown]
Based on clinical data, it is expected that subjects will experience a transient pain associated with the procedure of EP that dissipates shortly thereafter. EP-associated pain assessment monitoring

will be performed by the treating physician or designee (registered nurse, nurse practitioner, physician assistant) on Days 1 and 8 of each tavo-EP treatment visit before the EP procedure and 5 minutes after EP procedure. Only pain that persists five minutes after the end of EP procedure will be evaluated on numeric pain rating scale [Figure 1](#) and documented as an AE per the CTCAE v5.0.

Numeric pain rating scale measures the intensity or magnitude of sensations and subjective feelings and the relative strength of attitudes and opinions about specific stimuli, on a scale of 0 to 10 with a score of zero denoting "no pain at all" and a score of 10 denoting "worst possible pain" (Duncan, 1989; Holdgate, 2003; Johnson, 2005; Krebs, 2007).

Figure 1 Numeric Pain Rating Scale

0–10 Numeric Pain Rating Scale

8.2.4. Physical Examinations

- A complete physical examination will include, at a minimum, assessments of the Cardiovascular, Respiratory, Gastrointestinal and Neurological systems. Height and weight will also be measured and recorded.
- A brief physical examination will include, at a minimum, assessments of the skin, lungs, cardiovascular system, and abdomen (liver and spleen).
- Investigators should pay special attention to clinical signs related to previous serious illnesses.

8.2.5. Vital Signs

- Vital signs will be measured will include heart rate, respiratory rate, temperature, and blood pressure (systolic and diastolic).
- Blood pressure and heart rate will be done at rest as per standard practice at the investigational site.
- Significant findings noticed after the start of study medication and findings that worsen significantly, which meet the definition of an AE must be recorded on the AE eCRF.
- Height to be obtained at Screening only.

8.2.6. Clinical Safety Laboratory Assessments

- See Appendix 2 for the list of clinical laboratory tests to be performed and to the SoA (Section 1.3) for the timing and frequency.
- The investigator must review the laboratory report, document this review, and record any clinically relevant changes occurring during the study in the AE section of the case report form (CRF). The laboratory reports must be filed with the source documents. Clinically significant abnormal laboratory findings are those which are not associated with the underlying disease, unless judged by the investigator to be more severe than expected for the subject's condition.
- All laboratory tests with values considered clinically significantly abnormal during participation in the study or within 30 days after the last dose of study intervention should be repeated until the values return to normal or baseline or are no longer considered clinically significant by the investigator or principal investigator.
 - If such values do not return to normal/baseline within a period of time judged reasonable by the investigator, the etiology should be identified and the investigator notified.
 - All protocol-required laboratory assessments, as defined in Appendix 2, must be conducted in accordance with the protocol and the SoA.
 - If laboratory values from non-protocol specified laboratory assessments performed at the institution's local laboratory require a change in subject management or are considered clinically significant by the investigator (eg, SAE or AE or dose modification), then the results must be recorded in the CRF.

8.3. Adverse Events and Serious Adverse Events

The definitions of an AE or SAE can be found in Appendix 3 (Section 10.3).

AE will be reported by the subject (or, when appropriate, by a caregiver, surrogate, or the subject's legally authorized representative).

The investigator and any qualified designees are responsible for detecting, documenting, and recording events that meet the definition of an AE or SAE and remain responsible for following up AEs that are serious, considered related to the study intervention or study procedures, or that caused the subject to discontinue the study intervention (see Section 6.6).

8.3.1. Time Period and Frequency for Collecting AE, SAE and ECI Information

All SAEs will be collected from the signing of the ICF until the follow-up visit at the time points specified in the SoA (Section 1.3).

Table 3 below summarizes the different observation periods for AEs, SAEs, and ECIs.

Table 3: Adverse Event Observation Periods

Type of Event	Adverse Event	Serious Adverse Event	ECI with study intervention
Reporting period	From consent until 30 days after the end of treatment	From consent until 30 days after the last dose of study treatment for all SAEs, and any time after the end of study for SAEs believed to be related to study intervention	From consent until 30 days after the last dose of study treatment, or 30 days after the initiation of a new anti-cancer therapy, whichever is earlier
Reporting Timelines to the Study supporter	Entered into the clinical database on an ongoing basis	Within 24 hours	Within 24 hours

Medical occurrences that begin before the start of study intervention but after obtaining informed consent will be recorded on the Medical History/Current Medical Conditions section of the eCRF not the AE section.

The Investigator is responsible for ensuring that all AEs observed by the Investigator or reported by subjects are properly captured in the subject's medical records and reported in the eCRF.

Investigators are not obligated to actively seek AE, ECI or SAE after conclusion of the study participation. However, if the Investigator learns of any SAE, including a death, at any time after a subject has been discharged from the study, and he/she considers the event to be reasonably related to the study intervention or study participation, the Investigator must promptly notify the Study supporter.

8.3.2. Method of Detecting AEs and SAEs

The method of recording, evaluating, and assessing causality of AE and SAE and the procedures for completing and transmitting SAE reports are provided in Appendix 3 (Section 10.3).

During the study, subjects should be assessed for possible ECIs prior to each dose. Laboratory results should be evaluated and subjects should be asked for signs and symptoms suggestive of an immune-related event. Subjects who develop an ECI thought to be immune-related should have additional testing to rule out other etiologic causes. If laboratory results or symptoms indicate a possible immune-related ECI, then additional testing should be performed to rule out other etiologic causes. If no other cause is found, then it is assumed to be immune-related.

Care will be taken not to introduce bias when detecting AEs and/or SAEs. Open-ended and non-leading verbal questioning of the subject is the preferred method to inquire about AE occurrences.

8.3.3. Follow-up of AEs, ECIs and SAEs

After the initial AE/SAE report, the investigator is required to proactively follow each subject at subsequent visits/contacts. All SAEs, and ECIs (as defined in Section 10.3.3), will be followed until resolution, stabilization, the event is otherwise explained, or the subject is lost to follow-up (as defined in Section 7.3). Further information on follow-up procedures is given in Appendix 3.

8.3.4. Regulatory Reporting Requirements for SAEs

- Prompt notification by the investigator to the Sponsor of a SAE is essential so that legal obligations and ethical responsibilities towards the safety of subjects and the safety of a study intervention under clinical investigation are met.
- The Sponsor has a legal responsibility to notify both the local regulatory authority and other regulatory agencies about the safety of a study intervention under clinical investigation. The Sponsor will comply with country-specific regulatory requirements relating to safety reporting to the regulatory authority, Institutional Review Boards (IRB)/Independent Ethics Committees (IEC), and investigators.
- Investigator safety reports must be prepared for suspected unexpected serious adverse reactions (SUSAR) according to local regulatory requirements and forwarded to investigators as necessary.
- An investigator who receives an investigator safety report describing a SAE or other specific safety information (e.g., summary or listing of SAEs) from the Sponsor-investigator will review and then file it along with the Investigator's Brochure and will notify the IRB/IEC, if appropriate according to local requirements.
- Any serious adverse event, or follow up to a serious adverse event, including death due to any cause whether or not related to the study drug, must be submitted on an SAE form and assessed by PI in order to determine reporting criteria to regulatory authorities, IRB, **PMC**, FDA. Information about all SAEs is collected and recorded on the Serious Adverse Event Report Form; all applicable sections of the form must be completed in order to provide a clinically thorough report. The investigator (or designee; sub-investigator) must assess and record the relationship of each SAE to each specific study treatment (if there is more than one study treatment), complete the SAE Report Form, and submit the completed form.
- Each reoccurrence, complication, or progression of the original event should be reported as a follow-up to that event regardless of when it occurs. The follow-up information should describe whether the event has resolved or continues, if and how it was treated, whether the blind was broken or not, and whether the patient continued or withdrew from study participation.
- All SAE must be recorded on a MedWatch 3500 Form. SAE reports and any other relevant safety information are to be forwarded as follows,

MedWatch 3500 Reporting Guidelines:

Note: MedWatch 3500 forms and other information related to MedWatch reporting are available at <http://www.fda.gov/medwatch/index.html>.

A copy of all 15 Day Reports and Annual Progress Reports is submitted as required by FDA. Investigators will cross reference this submission according to local regulations to the Investigational Compound Number (IND, CSA, etc.) at the time of submission.

- An investigator (or designee; sub-investigator) will evaluate all adverse events according to the NCI Common Terminology for Adverse Events (CTCAE), version 5.0. Any adverse event which changes CTCAE grade over the course of a given episode will have each change of grade recorded on the adverse event case report forms/worksheets. All adverse events regardless of CTCAE grade must also be evaluated for seriousness.
- **Reporting Requirements for IND holder:**
 - For Investigator-sponsored IND studies, reporting requirements for the FDA apply in accordance with the guidance set forth in 21 CFR, Part 312.32. Events meeting the following criteria need to be submitted to the FDA as Expedited IND Safety Reports.
 - 7 Calendar-Day Telephone or Fax Report:

The Sponsor-Investigator is required to notify the FDA of a fatal or life-threatening adverse event that is unexpected and assessed by the investigator to be possibly related to the use of investigational agents. An unexpected adverse event is one that is not already described in the most recent Guidance for Investigator section of the Investigator's Brochure. Such reports are to be telephoned or faxed to the FDA, within 7 calendar days of the first learning of the event.
 - 15 Calendar-Day Written Report:

The Sponsor-Investigator is also required to notify the FDA and all participating investigators, in a written IND Safety Report, of any serious unexpected adverse event that is considered reasonably or possibly related to the use of investigational agent.

Written IND Safety Reports with analysis of similar events are to be submitted to the FDA, within 15 calendar days of first learning of the event. The FDA prefers these reports on a MedWatch 3500 Form but alternative formats (e.g., summary letter) are acceptable.

FDA Fax number of IND Safety Reports: [name].

The IND sponsor will also make an assessment of whether the event constitutes an unanticipated problem posing risks to subjects or others (UP). This assessment will be provided to the IRB, which, in turn will make a final determination. If the IRB determines an event is a UP it will notify the appropriate regulatory agencies and institutional officials.

All Adverse Events will be reported to regulatory authorities, IRB/IECs and investigators in accordance with all applicable global laws and regulations.

8.3.5. **Pregnancy**

- Details of all pregnancies in female subjects and, if indicated, female partners of male subjects will be collected after the start of study intervention and until through 5

months following cessation of study intervention, or 30 days following cessation of study intervention if the subject initiates new anticancer therapy, whichever is earlier.

- If a pregnancy is reported, the investigator should inform the Sponsor-investigator within 24 hours of learning of the pregnancy and should follow the procedures outlined in Appendix 4.
- Pregnancy should be followed up to determine outcome, including spontaneous or voluntary termination, details of birth, and the presence or absence of any birth defects or congenital abnormalities.
- Abnormal pregnancy outcomes (e.g., spontaneous abortion, fetal death, stillbirth, congenital anomalies, ectopic pregnancy) are considered SAEs.

8.3.6. Disease-Related Events and/or Disease-Related Outcomes Not Qualifying as AEs or SAEs

The following disease related events (DREs) are common in subjects with melanoma and can be serious/life threatening:

- Disease progression; if disease progression occurs, record the date first documented in the EOS visit eCRF. Signs and symptoms related to PD should be reported in the appropriate eCRF as an AE or as an SAE if the event in question meets the criteria for seriousness.

Because these events are typically associated with the disease under study, they will not be reported according to the standard process for expedited reporting of SAEs even though the event may meet the definition of a SAE. These events will be recorded on the corresponding eCRF page in the subject's CRF within the appropriate time frame.

In addition, the following will not be considered AEs

- Worsening of a pre-existing medical condition, (i.e., diabetes, migraine headaches, gout). However, it should be considered an AE if there is either a significant increase in severity, frequency, or duration of the condition or an association with significantly worse outcomes.
- Interventions for pretreatment conditions (i.e., elective cosmetic surgery) or medical procedures that were planned before study enrollment are not considered AEs.

NOTE: However, if either of the following conditions applies, then the event must be recorded and reported as an SAE (instead of a DRE):

- *The event is, in the Investigator's opinion, of greater intensity, frequency, or duration than expected for the individual subject.*

OR

- *The Investigator considers that there is a reasonable possibility that the event was related to study intervention.*

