10.3.1. Definition of AE

AE Definition

 • An AE is any untoward medical occurrence in a subject or clinical study subject, temporally associated with the use of study intervention, whether or not considered related to the study intervention. • NOTE: An AE can therefore be any unfavorable and unintended sign (including an abnormal laboratory finding), symptom, or disease (new or exacerbated) temporally associated with the use of study intervention.

Events Meeting the AE Definition

 • Any abnormal laboratory test results (hematology, clinical chemistry, or urinalysis) or other safety assessments (e.g., ECG, radiological scans, vital signs measurements), including those that worsen from baseline, considered clinically significant in the medical and scientific judgment of the Investigator (i.e., not related to progression of underlying disease). • Worsening of a pre-existing medical condition, (i.e., diabetes, migraine headaches, gout) should be considered an AE if there is either an increase in severity, frequency, or duration of the condition or an association with significantly worse outcomes. • New conditions detected or diagnosed after study intervention administration even though it may have been present before the start of the study. • Signs, symptoms, or the clinical sequelae of a suspected drug-drug interaction. • Signs, symptoms, or the clinical sequelae of a suspected overdose of either study intervention or a concomitant medication. Overdose per se will not be reported as an AE/SAE unless it is an intentional overdose taken with possible suicidal/self-harming intent. Such overdoses should be reported regardless of sequelae.

Events NOT Meeting the AE Definition

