
AE severity will be evaluated by the Investigator in accordance with the NCI CTCAE v5.0. For AEs that are not adequately addressed in the NCI CTCAE, the Investigator should classify the intensity of the AE using the following guidelines:
 
 Grade 1: Mild: Aware of sign or symptom, but easily tolerated; no intervention needed Grade 2: Moderate: Discomfort enough to cause interference with usual activity, minimal non-invasive intervention indicated (e.g., short course of antibiotics) Grade 3: Severe: Medically significant but not immediately life-threatening; incapacitation with inability to work or do usual activity Grade 4: Life-threatening: Refers to an event in which the subject was at risk of death at the time of the event, as judged by the Investigator; urgent/emergent intervention indicated. This category should not be used for an event that hypothetically might have caused death if it were more severe. Grade 5: Fatal outcome. 
It will be left to the Investigator's clinical judgment to determine whether an AE is of sufficient severity to require the subject's removal from treatment or from the study. A subject may also voluntarily withdraw consent from treatment due to what she/he perceives as an intolerable AE. If either of these situations arises, the subject should be strongly encouraged to undergo an end-of-study assessment and be under medical supervision until symptoms cease or the condition becomes stable. An event is defined as 'serious' when it meets at least 1 of the predefined outcomes as described in the definition of an SAE, NOT when it is rated as severe.

Assessment of Causality	

 The investigator is obligated to assess the relationship between study intervention and each occurrence of each AE/SAE as follows: 	
CAUSALITY	ASSESSMENT CRITERIA (all points should be reasonably complied with)
Not related	An AE with sufficient evidence to accept that there is improbable relationship to investigational product administration (e.g., no temporal relationship to drug administration) and the disease, other drugs or other events provide plausible explanation)
Possibly related	An AE with a reasonable time sequence to administration of the investigational product, but which could also be explained by concurrent disease or other drugs or events. Information on drug withdrawal may be lacking or unclear

Assessment of Causality	

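### The NOTE in section 8.3.6 makes a disease-related event an SAE without requiring a seriousness criterion, which conflicts with Appendix 3 and leaves SAE classification open to inconsistency

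*Combined protocol and SAP*

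**What the plan says.** Section 8.3.6 lists one DRE, disease progression. Its signs and symptoms are to be "reported in the appropriate eCRF as an AE or as an SAE if the event in question meets the criteria for seriousness". DREs are then exempted from the usual expedited SAE process, "even though the event may meet the definition of a SAE". A separate list follows of things that are not AEs: worsening of a pre-existing condition (diabetes, migraine and gout are the examples) and planned or elective interventions. The first of these has its own exception: "it should be considered an AE if there is either a significant increase in severity, frequency, or duration of the condition".

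The NOTE closes the section: "if either of the following conditions applies, then the event must be recorded and reported as an SAE (instead of a DRE". Condition one is that the event is, in the investigator's opinion, "of greater intensity, frequency, or duration than expected for the individual subject". Condition two is that "there is a reasonable possibility that the event was related to study intervention".

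Appendix 3 defines seriousness differently. Section 10.3.2 lists outcomes: death, threat to life, hospitalization, disability, congenital anomaly, and other important medical events by judgment. Section 10.3.5 adds that the label applies to an event "when it meets at least 1 of the predefined outcomes as described in the definition of an SAE, NOT when it is rated as severe". Section 10.3.1 says that worsening of a pre-existing condition "should be considered an AE if there is either an increase in severity, frequency, or duration of the condition".

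**The concern.** The NOTE is mandatory, and either condition is enough. Both describe how an event compares with expectation or what may have caused it; neither describes its outcome. An investigator who follows the NOTE to the letter could enter a non-serious event as an SAE, while one who follows Appendix 3 would enter the same event as an AE.

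Frequency, duration and severity of SAEs is a secondary safety endpoint (section 3), and SAEs are tabulated (section 9.4.4). SAE status also carries 24-hour reporting (Table 3 in 8.3.1), an SAE form, and assessment for reporting to the IRB, the Protocol Monitoring Committee and the FDA (8.3.4). The relatedness condition matters most for reporting. Section 8.3.4 requires a 15-day written IND safety report for serious, unexpected, possibly related events, so a non-serious related event labelled an SAE could enter that route.

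**Working it through.** No figure in the plan depends on this point, so there is none to reproduce. The check sets the texts side by side and then sizes one misclassified subject.

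**1. What makes an event an SAE, place by place**

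- 8.3.6, signs and symptoms of progression: an AE, or an SAE if the seriousness criteria are met.
- 8.3.6, pre-existing condition: an AE on a significant increase in severity, frequency or duration. Nothing is said about SAE.
- 8.3.6, NOTE: an SAE on greater intensity, frequency or duration than expected, or on possible relatedness. No seriousness criterion is stated.
- 10.3.1: the disease under study and its expected symptoms are not AEs unless more severe than expected. Nothing makes the more severe ones SAEs.
- 10.3.2: an SAE by listed outcome, and only if the event is first an AE.
- 10.3.5: serious by outcome, not by severity.
- 8.3.4: every AE, whatever its grade, must be evaluated for seriousness.

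Nearly the same trigger (worse than expected) thus leads to an AE in 10.3.1 and to an SAE in the NOTE. Relatedness and unexpected frequency or duration are not on the 10.3.2 list.

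**2. Which rule prevails**

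The plan does not say. Section 8.3.4 requires the seriousness evaluation but does not say what happens when it is negative and the NOTE applies.

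**3. Scope of the NOTE**

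The parenthesis in the NOTE points to DREs, and progression is the only DRE listed. But the NOTE comes directly after the bullets on pre-existing conditions and planned interventions, refers only to the event, and its first condition resembles the wording of the pre-existing-condition bullet. Whether it covers DREs alone is therefore unclear.

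**4. Size per subject**

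Inputs: maximum enrollment 33 and Stage 1 size 22 (section 9.2). The safety population is treated subjects (section 9.3); I assume all enrolled subjects were treated.

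- Shift in SAE incidence = misclassified subjects with no other SAE ÷ N.
- One subject of 33: 1/33 = 3.0 percentage points.
- One subject of 22, had the trial stopped at Stage 1: 1/22 = 4.5 points.
- Assumed range of one to three subjects of 33: 1/33 = 3.0 to 3/33 = 9.1 points.

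The range is for scale only. The documents give no rate of such events.

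**The case against.** The strongest reply is that the NOTE can be read coherently. DREs are introduced as events that can be serious, and the exemption concerns events that may already meet the SAE definition. In sequence, the NOTE merely returns those events to SAE reporting when they are unexpected or related, and creates no SAE from a non-serious event. Sections 8.3 and 8.3.2 send definitions and evaluation to Appendix 3, and 8.3.4 requires a seriousness evaluation for every AE.

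That reading is plausible and may be what was intended. But the NOTE does not state it: the section says only that DREs can be serious and may meet the definition, while the NOTE says that the event must be reported as an SAE. Nothing gives Appendix 3 precedence.

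Other parts of the reply stand, and they limit the point:

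- A reader might infer that any disease-related or pre-existing-condition event becomes an SAE. The text does not support that. A condition must be met, the parenthesis refers to DREs, and the pre-existing-condition bullet leads to an AE. A migraine flare has its own specific rule, and so has a symptom of progression.
- A reader might infer that the SAE rate is inflated. That is not shown; it is a risk whose size is unknown.
- A reader might infer that the SAE rate can no longer be compared with earlier tavo-EP experience. Section 2.3 gives individual events and no overall SAE rate, and the plan makes no such comparison.
- Any error of this kind runs toward over-reporting, and all patients have completed the neoadjuvant phase (note to section 1.3), so rewording now affects mainly adjuvant-phase and later events.

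**Conclusion.** The contradiction is real and can be checked on the page. Taken literally, the NOTE classifies a disease-related event as an SAE on unexpected intensity, frequency or duration, or on possible relatedness, without a seriousness criterion. That is at odds with 10.3.2, with 10.3.5 and with the seriousness condition earlier in 8.3.6, and its scope is unclear. The consequence is possible inconsistency in SAE counts and reporting, at 3.0 percentage points of incidence per misclassified subject if 33 are treated. How many subjects are affected, if any, cannot be found from the documents. The endpoint is descriptive and secondary; the pCR test, sample size and Stage 1 rule do not depend on it. The correction is worth making because it is nearly free and the rule as written can misclassify a stated endpoint.

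**What to change.** Reword the NOTE in two respects. State that it applies to DREs only. State that a DRE meeting either condition loses the exemption and goes through the standard process: recorded as an AE, and reported as an SAE if it meets a criterion in 10.3.2, including the medical-judgment criterion for important medical events. Events that are already serious would still be reported as SAEs.

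Before the safety tables are produced, list every SAE entered under the NOTE that has no recorded seriousness criterion, and query the investigator. Do not reclassify automatically: because one 10.3.2 criterion rests on judgment, the lack of a recorded outcome does not show that an event was non-serious, and demoting it by a listing rule could understate harm. The check can be written into the SAP, which section 9.4 says is to be finalized before database lock. With neoadjuvant treatment complete, this is the more useful half of the fix.

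The cost is a short wording change and a small listing and query task, with no new assessments of subjects.
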